**For missing or partial dates:**

- Missing dates for Day 30, 60, and Day 90 Visits will be imputed for the calculation of product use exposure within periods by adding 30, 60, or 90 days to the randomization date. If the imputed date falls after discharge date (e.g. for early terminated subjects), then the discharge date will be used.
- Missing or Partial dates will not be imputed for Adverse Events (AEs), for medical history, and for concomitant medications, but assumptions will be made as follows to assign them to specific analysis categories:

Date information (*)	AE Category	Disease Category	Medication Category
Missing date or Partial date, (e.g., --May2012, or ---2011) if month/year is the same as, or later than the month and/or year of Screening.	Product-emergent	Concomitant disease	Concomitant medication
Partial date, (e.g., --May2012, or ---2011). If month and/or year is earlier than the month and/or year of Screening.	Not product-emergent	Medical history	Prior medication

(\*) Missing or partial date refers to stop date for disease and medication categories

#### **12.1.5.1 Insufficient Data for Analysis/Presentation**

If there are no values or events at the general value then the break out should not be presented. For example if the number of AEs related to study procedure is zero then the presentation by severity of related events will not be produced.

Some of the TFLs will not have sufficient numbers of subjects or data for presentation. If this occurs, the blank TFL shell will be presented with a message printed in the center of the table, such as, “No serious adverse events occurred for this study.”

For categories of summaries that have <4 subjects no summaries will be shown.

#### **12.1.6 Handling of Unplanned Data**

Unscheduled post-product use readings will be excluded from the summary statistics. Unscheduled readings will be labelled as unscheduled in the listings and mapped to the relative study day using the date of the study day until midnight.

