7.7.1 Blood samples

Venous blood samples will be collected by qualified and trained site personnel. Subjects should be in a seated position during blood collection. The maximal total volume of blood drawn for each subject will be around 310 mL, which includes 40 mL for safety and repeated analysis, 30 mL of blood for long term storage of the bio-banking samples for further analysis of BoExp and risk markers (only if additional consents are given) and 15 mL for long-term storage bio-banking samples for further analysis of transcriptomics (only if additional consents are given) (Section 7.7.3).

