8.6 Adverse Events Leading to Withdrawal

Subjects who are withdrawn from the study because of an AE will undergo the safety procedures (see Section 9.5), as described for the day of Discharge, as soon as possible and will enter the period of safety follow-up. The Investigator or designee and/or [REDACTED] will follow up these AEs until they have resolved, stabilized (i.e., no worsening of condition), or an acceptable explanation has been found.

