## 12 PLANNED STATISTICAL METHODS

### 12.1 General Considerations

Data analysis will be performed using SAS® Version 9.3.

Data listings will be provided for all data collected as defined in the protocol, ordered by randomization arm and subject, Day, Visit and time point (if applicable), unless otherwise stated. Summary statistics and statistical analysis will only be presented for data where detailed in this SAP. All unscheduled assessments will be included in the listings.

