#### 12.1.3 Descriptive Statistics

For continuous data, summary statistics will include the number of subjects (n), the number and percent of subjects with missing data, the arithmetic mean, arithmetic standard deviation (SD), 95% confidence interval (CI), median, first and third quartiles, minimum and maximum; for log-normal data the geometric mean, geometric 95% CI and geometric coefficient of variation (CV) will also be presented. For categorical data, frequency counts and percentages will be presented. Data listings will include all subject level data collected unless otherwise specified.

Unless otherwise specified, data described over time will be reported for periods 2-4 (see **Table 25**).

Data for early termination will be summarized at the end of the corresponding period (1-4). Data for early termination collected during an unplanned ambulatory visit will be handled as specified in Section 12.1.6 “Handling of Unplanned Data”.

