#### 12.6.4.2.4 Laboratory Abnormalities

The shift in toxicity grades from baseline to worst grade recorded while in the exposure period will be presented in tables for the clinical chemistry, hematology and urinalysis parameters. Details related to the toxicity grading of laboratory abnormalities are available in Section 12.6.4.3 “Clinical laboratory Evaluation”.

The data will be presented in the below outputs:

TFL number	Title
TABLES	
15.2.6.16	Summary of Clinical Chemistry Parameters – Safety Population
15.2.6.17	Summary of Hematology Parameters – Safety Population
15.2.6.18	Summary of Urinalysis Parameters – Safety Population

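### By-visit safety summaries leave out unscheduled readings and unplanned ambulatory early-termination data, and for laboratory data this rule conflicts with the promised worst-grade shift

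*SAP*

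**What the plan says.** SAP 12.1.6 sets the general rule: "Unscheduled post-product use readings will be excluded from the summary statistics". The readings are kept elsewhere: "Unscheduled readings will be labelled as unscheduled in the listings and mapped to the relative study day". SAP 12.1 confirms this: "All unscheduled assessments will be included in the listings".

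SAP 12.1.3 has two consecutive sentences on early termination. The first says "Data for early termination will be summarized at the end of the corresponding period (1-4"); Table 25 defines period 1 as confinement and periods 2 to 4 as ambulatory. The second carves out an exception: "Data for early termination collected during an unplanned ambulatory visit will be handled as specified in Section 12.1.6".

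Two other SAP statements bear on the same data. The safety-summaries part of 12.1.3 describes the randomized period as baseline plus everything collected after it, with no exception for unscheduled values. Section 12.6.4.2.4 says "The shift in toxicity grades from baseline to worst grade recorded while in the exposure period will be presented in tables", without limiting this to scheduled visits.

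On collection, Protocol 5.1.3 requires the Day 6 safety examination as soon as possible after any withdrawal, in either period, unless the subject refuses it. Protocol 8.6 repeats this for one group: "Subjects who are withdrawn from the study because of an AE will undergo the safety procedures". Protocol 9.5 lists the content, which includes laboratory tests, physical examination, full lung function, vital signs and ECG.

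**The concern.** The withdrawal examination is the last safety examination the protocol requires of a subject who leaves early. The plan collects it and then, for most subjects who leave between ambulatory visits, keeps it out of the by-arm summaries of measured values. Whether a reading is omitted depends on whether the subject withdrew, and withdrawal for an adverse event is one route, so the omission may be informative. The by-visit tables then describe subjects who reached planned visits.

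The laboratory tables raise a separate problem. A worst-grade shift is meant to catch the worst value whenever it occurred. If it is built only from scheduled visits, it no longer does so. The SAP does not say which rule prevails, so two programmers could produce different tables, each with support in the text.

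**Working it through.** The plan gives no figure for unscheduled readings or unplanned early-termination visits, so there is none to reproduce. The check is a comparison of sections, with one illustrative calculation.

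**1. How often a withdrawal examination would be unplanned.** Inputs: discharge from confinement on Day 6 and final discharge on Day 91 (Protocol 4.4); on-site days 30, 31, 60, 61, 90 and 91 (Protocol 4.1); a window of plus or minus 5 days per visit (Protocol 9.3). Assumption: withdrawals are spread evenly over the ambulatory period. The documents give no withdrawal rate or timing.

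- Length: 91 − 6 = 85 days.
- Counting only nominal on-site days as planned: (85 − 6)/85 = 79/85 = 92.9%.
- Counting every window day as planned: Days 25–36, 55–66 and 85–91 give 12 + 12 + 7 = 31 days; (85 − 31)/85 = 54/85 = 63.5%.
- The protocol counts 86 ambulatory days, including both end days. Then 80/86 = 93.0% and 55/86 = 64.0%, the same after rounding.

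These are fractions of calendar days. They show that the exception in 12.1.3 would apply to the usual case. They do not count lost readings.

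**2. What each table section does with such a reading.**

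- ECG (SAP 12.6.4.4.5): summarised at baseline, Day 6 and the Day 30, 60 and 90 Visits. An unplanned examination has no place in the table.
- Lung function (12.6.4.4.4): summarised in the randomized period at Baseline, Day 6 and the Day 90 Visit. Same result.
- Vital signs (12.6.4.4.3): summarised by study day. Rule 12.1.6 removes the unscheduled reading.
- None of these three sections defines a worst post-baseline summary that would pick the reading up.
- Laboratory (12.6.4.3 and 12.6.4.2.4): both use tables 15.2.6.16 to 15.2.6.18. The first lists named visits; the second asks for the worst grade in the exposure period. The SAP's list of special terms runs the exposure period from Day 1 to discharge on Day 91, so an examination between visits falls inside it. Rule 12.1.6 would take it out again.

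**3. Direction of the laboratory effect.** A subject's worst grade over scheduled visits is a maximum over a subset of that subject's exposure-period readings. It is less than or equal to the maximum over all of them. Applying 12.1.6 can therefore lower the reported worst grade or leave it unchanged, and never raises it.

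**4. What the rule does not touch.** Early-termination data from confinement are summarised at the end of period 1. Only unscheduled readings taken after product use are excluded. Protocol 8.4.1 requires Grade 2 and higher laboratory values to be reported as, or linked to, an AE or concomitant disease, and Protocol 8.2.4 makes new clinically relevant abnormal findings AEs.

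**The case against.** Leaving unscheduled readings out of by-visit descriptive statistics is ordinary practice. SAP 12.1.3 uses the term summary statistics for continuous data and describes categorical data separately as counts and percentages, so 12.1.6 may never have been meant to reach a categorical shift table. AE data are the primary safety assessment (Protocol 12.6.5), clinically relevant abnormalities reach them, and AEs leading to discontinuation have their own tables. Few subjects may be affected.

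Much of this stands. By-visit means should stay on scheduled data, and the laboratory omission is a possible reading, not a settled one. But the SAP does not state the narrow reading, and the exception in 12.1.3 removes what the preceding sentence grants. Listings and AE terms do not replace by-arm summaries of measured values.

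Three stronger inferences are tempting and not supported:

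- That these readings appear in no safety table at all. The worst-grade and all-post-baseline statements leave the laboratory tables open.
- That the readings were taken because something went wrong, with unequal loss across arms. Protocol 5.1.3 also lists consent withdrawal, non-compliance and study termination among the reasons for leaving, and nothing in the documents shows that reasons differ by arm. The blood allowance of "40 mL for safety and repeated analysis" shows that repeat analysis was foreseen; it does not mention for-cause testing.
- That 64% to 93% of withdrawal examinations are lost. Those figures rest on assumed uniform withdrawal times.

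**Conclusion.** The concern holds in a limited form. As written, SAP 12.1.3 and 12.1.6 keep the withdrawal examination of most subjects who leave between ambulatory visits out of the by-visit ECG, vital-sign and lung-function summaries. For laboratory data they conflict with the SAP's own worst-grade and all-post-baseline statements, and if the exclusion prevails the worst grade is understated wherever an excluded reading was the worst.

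The size cannot be stated as a number of readings or subjects. That most such examinations would be unplanned rests on the as-soon-as-possible requirement and on the calendar, under the even-spread assumption. Listings and AE reporting limit the harm: clinically relevant findings are not lost from the report. What is missing is their measured values in the arm-level summaries. The primary biomarker endpoints are not at issue.

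**What to change.** Make three changes to the SAP text:

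1. In 12.1.6, limit the exclusion to by-visit means and changes from baseline.
2. In 12.6.4.2.4, state that the worst-grade laboratory shift in tables 15.2.6.16 to 15.2.6.18 uses all exposure-period readings: scheduled, unscheduled and early termination.
3. In 12.1.3, remove the unplanned-visit exception for safety data, so that early-termination safety data are summarised at the end of the corresponding period, as the sentence before it already says.

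Together these bring 12.1.3, 12.1.6 and 12.6.4.2.4 into agreement. No new data are needed. The cost is a few sentences and a small programming change. Some early-termination rows will be sparse; lung function, for example, has no scheduled summary at the end of periods 2 and 3. The rule in 12.1.5.1 against showing summaries for fewer than 4 subjects may suppress some of them. Worst-value tables for ECG or vital signs do not exist in the plan; adding them is optional and not part of this fix.

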#### **12.1.7 Multiple Comparisons / Multiplicity**

The primary endpoints will be tested using a multiple testing procedure to preserve the overall alpha level by simultaneously testing the endpoints using a closed procedure with each test performed at an alpha level of 5%. This implies that statistical significance is required for all primary endpoints in order to be able to make confirmatory claims about any of the endpoints.

No adjustment will be made on any of the secondary endpoints.

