12.1.5 Significance Level for Inferential Analysis

Unless stated otherwise, all statistical tests will be two-sided and conducted at the 5% level, and all quoted confidence intervals will be two-sided 95% confidence intervals.

The primary endpoints will be tested using a multiple testing procedure to preserve the overall alpha level by simultaneously testing the endpoints using a closed procedure with each test performed at an one-sided alpha level of 2.5%. This implies that statistical significance is required for all primary endpoints in order to be able to make confirmatory claims about any of the endpoints.

Further details will be provided in the SAP.

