##### 5.5.2 Evaluation Criteria

The study will be considered successful if the study demonstrates a 50% reduction or more in MHBMA, 3-HPMA, S-PMA, and COHb on Day 5, and in Total NNAL at the Day 90 Visit in smokers switching from mCC to THS 2.2 Menthol as compared to smokers continuing to smoke mCC, using a one-sided test with 2.5% type I error probability.

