**Table 20: Expected Power (YVD-CS01-EU and ZRHX-EX-01 Studies Assumptions)**

Assumptions	Reduction					
	50%	51%	52%	53%	54%	55%
YVD-CS01-EU	94%	88%	81%	70%	56%	38%
ZRHX-EX-01	98%	97%	92%	76%	41%	6%

A total of 160 smokers (80 in THS 2.2 menthol, 40 in mCC, and 40 in the SA arm) will be randomized to demonstrate a reduction of at least 50% on 5 primary BoExp in smokers switching from mCC to THS 2.2 Menthol as compared to those continuing to smoke mCC, using one-sided test with 2.5% type I error probability.

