### 12.6.1 Primary Analyses

#### 12.6.1.1 Analysis of Biomarkers of Exposure for Primary Endpoints

The BoExp (COHb in blood and urinary concentrations of MHBMA, 3-HPMA, S-PMA and Total NNAL) used for the primary analysis will be summarized as detailed in Section 12.1.3 “Descriptive Statistics”. The listing of the COHb data will have a flag for whether a subject’s COHb was <2%.

The baseline is as defined in Section 12.1.4 “Definitions for Statistical Data Analysis”.

The primary endpoints will be log-transformed (basee) prior to analysis. The analysis will compare the evening COHb level (20:00-21:30 PM) on Day 5; and urinary concentrations of MHBMA, 3-HPMA and S-PMA adjusted for creatinine on Day 5 and urinary concentrations of Total NNAL adjusted for creatinine on Day 90 Visit between the THS 2.2 Menthol and mCC arms for the PP Set. An analysis of covariance (ANCOVA) (Snedecor and Cochran 1982) model will be used with terms for the log-transformed baseline value, sex, average daily mCC consumption over the last 4 weeks as reported during screening and randomization arm.

The SAS code to be used for the THS 2.2 Menthol and mCC data is shown below:

```
Proc glm data=_data_;
Class randomization_arm sex cigarette_cons;
Model log_biomarker = log_baseline sex cigarette_cons
randomization_arm;
Lsmean randomization_arm / pdiff =control('mCC') alpha=0.05 cl;
Run;
```

The least squares (LS) means and estimate of the difference and the 95% CI will be back-transformed. The geometric LS means for each randomization arm along with the ratio

(THS 2.2 Menthol : mCC), two-sided 95% CI and one-sided p-value will be presented in the tables. THS 2.2 menthol : mCC effects will be graphed in a forest plot.

All figures, summaries and analyses will be performed on the PP Set. Additional descriptive statistics will be provided within the secondary analysis.

The data will be presented in the below outputs:

TFL number	Title
FIGURES	
15.1.1.1	Forest Plot of Statistical Analysis of Biomarkers of Exposure on Day 5 and Day 90 – PP Set
15.1.1.2	Biomarkers of Exposure Geometric Mean and 95% CI – PP Set
TABLES	
15.2.3.1.1	Analysis of COHb, MHBMA, 3-HPMA, S-PMA and Total NNAL on Day 5/90 Visit for THS 2.2 Menthol versus mCC for the Primary Objective – PP Set
15.2.4.1.1	Descriptive Statistics of Blood COHb (%) – PP Set
15.2.4.1.1.1	Descriptive Statistics of Blood COHb (%) by Sex – PP Set

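### SAP 12.1.7 sets the primary test level at 5% without stating sidedness, where the protocol and the SAP's own success criterion use one-sided 2.5%

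*SAP*

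**What the plan says.** Protocol 12.1.5 sets a general default, "Unless stated otherwise, all statistical tests will be two-sided and conducted at the 5% level", and then makes an exception for the primary endpoints, "each test performed at an one-sided alpha level of 2.5" per cent.

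SAP 12.1.7 carries the same paragraph, including the requirement that all five endpoints be significant, but its level reads "simultaneously testing the endpoints using a closed procedure with each test performed at an alpha level of 5" per cent. The words fixing the side are gone and the number has changed.

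Elsewhere the SAP keeps the protocol's level:

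- The success criterion in 5.5.2 asks for a reduction of at least 50% in all five biomarkers, "using a one-sided test with 2.5% type I error probability".
- The sample-size justification in section 8 computes power "using one-sided test with 2.5% type I error probability".
- The cut-offs given for one-sided p-values in 12.6.2.1 (secondary biomarkers), 12.6.2.4 (CYP1A2) and 12.6.3.4 (CYP2A6) are all 0.025.

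The primary analysis in 12.6.1.1 promises "two-sided 95% CI and one-sided p-value will be presented in the tables" but attaches no cut-off to that p-value. Its code line is "Lsmean randomization_arm / pdiff =control('mCC') alpha=0.05 cl".

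Neither the SAP revision history (3.1) nor section 9, on changes from the protocol analysis, mentions a change of level.

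**The concern.** SAP 12.1.7 is where the confirmatory rule for the primary endpoints is stated, and 5% is the only level the SAP's methods section attaches to those tests. The p-value in the primary table is one-sided. A programmer or report author working from 12.1.7 and 12.6.1.1 alone could compare that p-value with 0.05.

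The SAP does not block this reading. Its general considerations (12.1) give no default sidedness, and the protocol's two-sided default gives way where something else is stated, as protocol 12.1.5 does for these endpoints. On that reading the primary endpoints would have a looser cut-off than the secondary biomarkers. A result in the gap would succeed under one section of the SAP and fail under another. Success needs all five endpoints, so one result in the gap can settle the study verdict.

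**Working it through.** **Inputs.** Mean ratios and CVs come from SAP Tables 16 to 18, sample sizes from Table 19 (80:40 for the Day 5 endpoints, 40:40 for Total NNAL), stated power from Table 20, and the 0.50 margin from 5.5.2. Log-normal data and independent endpoints are assumed, because the documents give neither the joint-power method nor the correlations.

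**Critical values.** One-sided 2.5%: 1.960. Two-sided 5%: 1.960. One-sided 5%: 1.645. The first two are the same test in the direction of benefit.

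**Formulas.** SD on the log scale = √ln(1 + CV²). SE = SD × √(1/n₁ + 1/n₂). Power = Φ(ln(0.50/MR)/SE − critical value).

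**The plan's own figure, YVD-CS01-EU assumptions, 50% reduction**

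- COHb (0.40, CV 0.32, 80:40): SD = √ln(1.1024) = 0.3122; SE = 0.3122 × √(1/80 + 1/40) = 0.0605; ln(0.50/0.40)/SE = 3.69; power = Φ(3.69 − 1.960) = 0.958.
- Total NNAL (0.30, CV 0.60, 40:40): SD = √ln(1.36) = 0.5545; SE = 0.5545 × √(2/40) = 0.1240; ln(0.50/0.30)/SE = 4.12; power = Φ(4.12 − 1.960) = 0.985.
- 3-HPMA, MHBMA and S-PMA: 0.9999 or higher.

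The joint power is the product of the five.

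| Assumptions | Stated | One-sided 2.5% (= two-sided 5%) | One-sided 5% |
|---|---|---|---|
| YVD-CS01-EU | 94% | 94.3% | 97.3% |
| ZRHX-EX-01 | 98% | 98.2% | 99.2% |

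The YVD-CS01-EU row matches only the one-sided 2.5% reading, and so do its 51% and 52% columns within 2 points. The ZRHX-EX-01 row does not separate the readings at 50%. Its 52% and 53% columns (stated 92% and 76%) come closer at one-sided 5% (92.8% and 76.9%) than at 2.5% (86.7% and 65.3%). Several columns for larger reductions are not reproduced on either reading. So the table supports the level stated in its text through the first row, not throughout.

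**Type I error of the all-five rule.** It is greatest when one endpoint sits exactly at 0.50 and the other four are almost certain to pass; it then approaches the level of the single test. Under the YVD-CS01-EU assumptions:

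- COHb at 0.50: 0.025 × 0.9999 × 0.9846 = 2.46%, against 0.05 × 0.9933 = 4.97% at one-sided 5%.
- Total NNAL at 0.50: 0.025 × 0.9582 × 0.9999 = 2.40%, against 0.05 × 0.9796 = 4.90%.

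The maximum is therefore 2.5% or 5.0%. Requiring all five endpoints does not remove the doubling.

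**Where the verdict would differ, COHb (SE 0.0605).**

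- One-sided 2.5%: pass if the observed ratio is below 0.50 × exp(−1.960 × 0.0605) = 0.444.
- One-sided 5%: pass if it is below 0.50 × exp(−1.645 × 0.0605) = 0.453.

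At the planned ratio of 0.40 the chance of landing between these limits is 97.96% − 95.82%, about 2 percentage points.

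**The case against.** The strongest reply is that 12.1.7 names no side and no p-value, and everything around it points to two-sided 5%. The protocol that the SAP supplements has a two-sided 5% default. The primary code and interval use 0.05 as a two-sided level. The SAP's own success criterion is one-sided 2.5%. No section sets a one-sided p-value against 0.05. Section 9, which exists to list changes, lists none here. On that reading there is one threshold, and only the label is missing. This stands, and it governs the severity.

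A second reply also stands. The code's comparison is of the two arm means, that is, against a ratio of 1, in line with the stated hypothesis that THS 2.2 Menthol is lower. A p-value from that test cannot decide the 50% criterion at any cut-off. The only primary output that can be set directly against 0.50 is the two-sided 95% CI, and its level is already right.

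What these replies do not do is supply the missing words. The SAP gives no two-sided default, the tabulated p-value is one-sided, and neither 12.1.7 nor 12.6.1.1 ties the test to 0.50.

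A reader might infer two stronger things that the documents do not support:

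- **That the SAP has relaxed the level and doubled the type I error.** This needs the one-sided reading of 12.1.7, which nothing else in the SAP shares.
- **That the accidental unblinding disclosed in section 9 lies behind the wording.** The documents do not show when the wording entered, and the revisions recorded after version 1.0 do not mention it.

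**Conclusion.** The point holds as a minor inconsistency in a decision threshold. SAP 12.1.7 departs from protocol 12.1.5 and SAP 5.5.2 without declaring it, and leaves the side of its 5% unstated next to a one-sided p-value with no cut-off.

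If the 5% is two-sided, the likely intent, the test, the power and the type I error are unchanged. If it is applied to a one-sided p-value, the maximum type I error of the all-five rule goes from 2.5% to 5.0%. That consequence is conditional on the reading, and also on the p-value being computed against 0.50. The COHb band additionally assumes log-normal data, CV 0.32, 80:40 subjects and no gain in precision from the covariates. Inflation is possible under one reading; it is not shown.

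**What to change.** Make two edits to the SAP:

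1. In 12.1.7, replace the unlabelled 5% with the protocol's level and give the equivalent interval rule: *every primary endpoint is tested one-sided at 2.5%; an endpoint succeeds if the upper limit of the two-sided 95% CI for the THS 2.2 Menthol:mCC ratio lies below 0.50.*
2. In 12.6.1.1, state that the one-sided p-value is computed against a ratio of 0.50 and judged at 0.025.

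The first edit removes the sidedness question and ties the confirmatory rule to the 50% margin. The second makes the tabulated p-value agree with it.

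The cost is two sentences and a matching adjustment to how the primary p-value is produced. Design, data collection, sample size and planned power are unaffected.
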